## 1. Specific Aims and Hypotheses

Enhancing message management and virtual urgent care options for patients are among TPMG and KFH's top priorities. As team-based inbox management is further developed, evaluating its clinical effectiveness and outcomes in terms of patient care experience and costs will provide valuable information for operational planning. In addition, sharing what we learn with other health care systems through talks and publications will help highlight TPMG's reputation as a group that innovates to support clinicians while increasing patient access through virtual care.

This study will compare the clinical outcomes and costs of two alternative modes of management of patient requests for Paxlovid sent via e-visits: management by a regional team of pharmacists, vs. management by medical center-based pools of adult and family medicine physicians (AFMs) doing desktop medicine. We will conduct a cluster randomized trial in 17 facilities in Kaiser Permanente Northern California to compare Pharmacist Care with AFM Pool Care for patients making Paxlovid e-visits with regard to:

Aim 1. Quality of care

Example hypothesis: Patients with common potential DDIs will be more likely to receive relevant counseling in the Pharmacist Care group than the AFM Pool Care group.

Aim 2. Clinician time and costs

Example hypothesis: Pharmacist Care will have lower costs of clinician time per Paxlovid e-visit managed than AFM Pool Care.

Aim 3. Exploratory outcomes

Example hypothesis: Patients in the Pharmacist Care will report comparable satisfaction with the process compared with the AFM Pool Care group.

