#### 4.4. Main outcomes and measures

#### 4.4.1. Outcomes

The primary outcome will be measured only among patients who have common potential drugdrug interactions (DDIs) based on a pre-specified list of medications. The outcome will be whether the patient received counseling for any valid potential DDI. For patients with more than one DDI, the outcome will counted as present if they received counseling for any of their potential DDIs.

Secondary outcomes will be:

- a. % of all patients who were prescribed Paxlovid (based on orders)
- b. Hours from the e-visit request to the prescription order being placed, among patients who were prescribed Paxlovid
- c. Clinician minutes per message handled. This will be analyzed using EPIC access log data. We will link each e-visit for Paxlovid with the relevant secure messages and/or

telephone encounters, including follow-ups that occurred before the initial request was resolved. Clinicians include pharmacists and physicians.

- d. Estimated personnel cost per Paxlovid message handled. The estimated cost per message handled will be calculated by multiplying the number of minutes spent per message by the standard wage rate for a pharmacist or AFM in Northern California.
- e. Patient satisfaction with care

Exploratory outcomes will be:

- a. Number of Paxlovid e-visits handled by the regional pharmacy team, per week
- b. % of messages fully handled by the initial clinician (pharmacist or AFM) (based on review of visits)
- c. % of cases handled by pharmacists that required a physician consultation (based on review of visits)
- d. Pharmacist satisfaction with the process of care [Note: Deleted "AFM satisfaction" as a measure because there was not a logical group of AFMs to survey, nor logical questions to ask them.]
- e. % of all patients who obtained Paxlovid (based on fills)
- f. Days from request to receipt of medication among patients prescribed Paxlovid
- g. % of patients with common potential DDIs who were prescribed Paxlovid
- h. If feasible based on ICD-9 codes: Incidence of drug reactions due to Paxlovid DDIs within 10 days after a Paxlovid prescription

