The pharmacist and physician surveys have been designed to require no more than 3 to 5 minutes to complete. These surveys will be fielded via Outlook email using a Teams form, as well as on paper via interoffice mail. A small gift to thank pharmacists and physicians for considering participation will be included in the mailing. Responses will be treated as confidential and data will be aggregated, with no individual identifiers associated with data presented in reports.

Data collected from both pharmacists AFMs and will include:

- a. Satisfaction with the process of care (on a 5-point scale)
- b. Suggestions for improving the care process (open-ended)

4.6. Statistical analysis plan.

During the survey and visit review components of this study, it became clear that more patients than projected had received pharmacist care. A preliminary analysis conducted on 12/18/2024, prior to evaluating any outcomes, found that the facility assigned to each e-visit usually did \*not\* match the home facility of the patient who initiated the e-visit. This was most likely due to an operational workflow (which is still being elucidated) that was unanticipated at the time this study was designed and facilities were assigned at random to the Pharmacist Care vs. Physician Care groups. Due to the fact that the patient's "home" facility became imbalanced, we will include this as a covariate in the primary analysis (see below).

The primary analysis will group each patient based on which type of clinician (pharmacist or physician) first accessed the eVisit. This is similar to a per-protocol analysis. A patient whose eVisit was first accessed by a pharmacist will be counted in the pharmacist group, even if the eVisit was referred to a physician. A patient whose eVisit was first accessed by a physician will be included in the physician group, even if the eVisit was referred to a physician group, even if the eVisit was referred to a physician group, even if the eVisit was referred to a pharmacist. We select this approach as the primary analysis because it best reflects what patients experience in real-life care delivery, which this study is intended to evaluate.

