A secondary analysis will treat each patient as part of the group to which they were assigned based on the facility listed on the e-visit worklist (intention-to-treat). However, this approach may be worse at reflecting the actual patient experience because dozens of pharmacists and physicians were involved in executing the randomization assignments. It is possible that some patients will have received a different mode of care from the group to which they were assigned.

The primary outcome is binary, i.e., whether or not a patient received counseling for a DDI. This will be compared between study groups using mixed effects logistic regression providing point and interval estimates of outcome odds ratios associated with study group. This analysis technique accounts for the within-facility correlation among patients to obtain valid estimates of treatment effects and associated standard errors. The pre-specified set of covariates for inclusion in regression models include: study group and covariates used in the randomization procedure (i.e. patient socioeconomic status (using the Neighborhood Deprivation Index), patient race/ethnicity, and service area level COVID-19 incidence). Study group and other covariates will be treated as fixed effects and the patient's home facility and e-visit facility will be handled as random effects.

In addition, exploratory/sensitivity analyses will examine the impact of including additional covariates in our estimation of treatment effect, with focus on variables with chance imbalance in distributions by treatment group, as determined in preliminary analyses. Analyses resulting in an appreciable change in the estimate of treatment differences or increased precision of the treatment effect will be noted.

For the secondary outcomes, we will compare the estimated cost per Paxlovid message, the minutes spent per message, and the hours from e-visit to prescription order between the Pharmacist Care and AFM Pool Care groups using linear mixed regression models, providing point and interval estimates of between-group differences in mean outcomes. If cost or minutes have a skewed distribution, log transformation will be used. Analyses of other secondary outcomes with that are continuous will be similar. The approach to inclusion of covariates and sensitivity/exploratory analyses is as described for Aim 1.

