Given the group-randomization study design, calculation of sample sizes and minimum detectable treatment effects must account for the expected intraclass correlation (ICC) of observations within facilities. The ICCs in outcomes of interest are expected to be quite small, and therefore we present minimum detectable effects for an expected ICC of .01.

For Aim 1, the primary outcome is the % of patients with common potential DDIs who received counseling. We conservatively estimate that 70% of patients in the Pharmacist Care group will have received DDI counseling. A clinically meaningful difference between the two groups would be a relative risk (RR) of 0.8, which corresponds to a small effect size. To attain 80% power to identify such an effect with a two-tailed alpha of 0.05 and an ICC of .01, we need a sample size of 250 in each group and will plan our review of text extracts from the EHR accordingly.

For Aim 2, the example hypothesis is that the cost of management per e-visit for Paxlovid will be lower in the Pharmacist Care group than in the AFM Pool Care group. Given a two-tailed alpha of .05, the sample size of this study has 80% power to identify an effect size of 0.20 standard deviation units, which is a relatively small effect size. In other words, this study will have good power to find a statistically significant difference between the Pharmacist Care and AFM Pool Care groups even if the effect is relatively small.

For the patient survey in Aim 3, the sample size is selected to balance power and feasibility. We aim to collect completed surveys from 200 patients in each of the two study groups. We

estimate a response rate of 60%. To obtain 200 completed surveys in each group, we estimate needing to attempt surveys with 333 patients in each group. The completed sample size of 200 in each group will give us good power to identify relatively small differences in satisfaction scores, which are measured on a continuous scale. We will be able to detect effect sizes of .31 relative to a standard deviation of 1.

The purpose of the pharmacist and AFM surveys is process assessment and performance improvement. These surveys will focus on qualitative, open-ended responses; thus, sample size and power are not estimated here. We will survey all pharmacists on the regional team providing Paxlovid e-visits (estimated n=10). We also will survey the AFMs who are Paxlovid e-visit site leads (estimated n=12).

Date	Operational team	Research team

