## 4.9 Timeline

## 4. Projected Impact

This study's findings quality of care, cost, and patient and clinician satisfaction will inform decisions about how to deploy pharmacist effort for KPNC. The study leaders include regional leaders for Virtual Medicine and Pharmacy who are well-positioned to make implementation decisions based on the results we generate.

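### Logging skewed cost and minutes changes the target from the mean to the geometric mean, so Aim 2 could report a saving or an excess that mean cost does not show

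*Combined protocol and SAP*

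**What the plan says.** Section 4.6 compares cost per message, minutes per message and hours to prescription with linear mixed models, "providing point and interval estimates of between-group differences in mean outcomes". The next sentence reads: "If cost or minutes have a skewed distribution, log transformation will be used". The section does not say how skewness will be judged, how a log-scale estimate will be back-transformed or labelled, or how zero minutes would be handled. It plans no companion result on the mean scale; its sensitivity analyses concern added covariates.

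The Aim 2 example hypothesis in section 1 is that "Pharmacist Care will have lower costs of clinician time per Paxlovid e-visit managed than AFM Pool Care". Section 4.4.1 obtains cost by "multiplying the number of minutes spent per message by the standard wage rate for a pharmacist or AFM in Northern California". The Projected Impact section says the findings "will inform decisions about how to deploy pharmacist effort for KPNC".

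The primary grouping in section 4.6 is by the clinician type that first opened the e-visit. A pharmacist-first patient "will be counted in the pharmacist group, even if the eVisit was referred to a physician". The same rule holds for physician-first patients, "even if the eVisit was referred to a pharmacist".

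**The concern.** The two adjacent sentences name different quantities. The first is a difference in arithmetic means. Exponentiating the group coefficient of the second gives a ratio of geometric means. For a staffing decision the relevant quantity is total clinician cost, which is volume times the arithmetic mean. The geometric mean gives little weight to the few long, expensive e-visits, and those count in full towards spending.

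The two ratios agree if the log-scale spread is equal in both groups. The documents give reasons to doubt that it is. One group is a regional team on a single protocol, while the other is medical-center pools that may also follow local protocols (section 4.2). Linked follow-up messages and calls count towards minutes (section 4.4.1). Referred e-visits stay in the first-access group and can carry two clinicians' time. Referrals can go either way, and no referral rates or standard deviations are given, so neither the size nor the direction of a difference in spread is known in advance.

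**Working it through.** **Inputs from the documents.** 1,560 e-visits, 17 facilities of about 92, ICC 0.01, two-sided alpha 0.05, and for Aim 2 a statement that "the sample size of this study has 80% power to identify an effect size of 0.20 standard deviation units" (section 4.8). Log-scale SDs are not given and are assumed below.

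**The plan's own figure.** Design effect = 1 + 91 × 0.01 = 1.91. With 1,560/2 = 780 per group, the effective n is 780/1.91 = 408. The minimum detectable effect is (1.96 + 0.84) × √(2/408) = 0.196 SD, and power at 0.20 SD is 81.5% by the normal approximation (76% with t on 15 df). The stated 80% at 0.20 SD is reproduced.

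**What the log model targets.** For lognormal cost with log-SDs s_A (AFM) and s_P (Pharmacist), the arithmetic mean is the geometric mean × exp(s²/2). If true mean costs are equal, the Pharmacist/AFM geometric-mean ratio is exp((s_A² − s_P²)/2).

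**Chance of a significant log-scale result when mean costs are equal.** SE = √((s_A² + s_P²) × 1.91/780); noncentral t with 17 − 2 = 15 df. For 0.6 vs 0.8: log ratio = (0.36 − 0.64)/2 = −0.140; SE = √(1.00 × 1.91/780) = 0.0495; z = −2.83.

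| s_A | s_P | Ratio | z | Significant | Shift in pooled log-SDs |
|---|---|---|---|---|---|
| 0.6 | 0.6 | 1.00 | 0 | 5% | 0 |
| 0.6 | 0.65 | 0.97 | −0.71 | 10% | 0.05 |
| 0.6 | 0.7 | 0.94 | −1.42 | 27% | 0.10 |
| 0.6 | 0.8 | 0.87 | −2.83 | 75% | 0.198 |
| 0.8 | 0.6 | 1.15 | +2.83 | 75% | 0.198 |

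In the last two rows the artefact is about as large as the 0.20 SD effect that the plan is powered to find.

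**Simulation.** With 8 vs 9 facilities of 92, ICC 0.01, equal true means, 4,000 runs and t-tests on facility means, the log scale was significant in 5.0%, 10.0%, 27.7%, 75.6% and 73.2% of runs, in table order. The untransformed scale stayed between 4.8% and 5.6%.

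**Sign reversal.** In a second simulation, with 408 effective independent observations per group, s_P = 1.0, s_A = 0.8 and true mean cost 10% *higher* with pharmacists, the ratio is 1.10 × exp((0.64 − 1.00)/2) = 0.92. A significant saving appeared in 26% of runs.

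**Can referral produce such spreads?** Assume log-SD 0.6 per clinician, and referral in one group only, adding an independent second clinician's time.

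- *Second minute priced the same, which is also the case for minutes:* 5% to 50% referral raises the log-SD to 0.62–0.66. The ratio moves by 1% to 3%.
- *Second minute twice as costly:* 10% referral gives log-SD 0.68, ratio 0.94 and 27% significant; 20% gives 0.74, 0.90 and 52%.
- *Three times as costly:* 10% gives 0.73, 0.89 and 65%; 20% gives 0.82, 0.84 and 92%.

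If referred e-visits instead take a fixed multiple of the usual time, minutes can move further. For 10% at twice the time the ratio is 2^0.1/1.1 = 0.97; for 20% at three times it is 3^0.2/1.4 = 0.89.

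**The case against.** The strongest reply is that the harm is doubly conditional: the data must be skewed enough to trigger the rule, and the spreads must differ. With equal spreads the log analysis is unbiased for the ratio and only the reporting scale changes. That is correct, and it is why the conclusion is that Aim 2 *could* mislead.

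Second, the 0.6 vs 0.8 row and its match to 0.20 SD come from the choice of SDs. For minutes, adding a second clinician's ordinary time does not get near that row. This also stands: for minutes the distortion from that mechanism is small. For cost, the larger rows are reached only if the second clinician's minute costs two to three times as much. The plan gives no wage rates and no rule for pricing a message that two clinicians handled.

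Third, the percentages use 17 facilities as randomised, whereas the primary analysis groups by first access with two facility random effects. They therefore indicate scale only. The shift in the target does not depend on the design.

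Fourth, analysing raw costs loses precision, most of all when skew is strong. That is a real cost, quantified under the fix. Greater precision for the geometric-mean ratio does not answer a question about mean cost.

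**Conclusion.** The concern holds. Followed as written, the log rule replaces the promised difference in means with a ratio of geometric means, and nothing in the plan brings the result back to the mean scale. With equal true mean cost, the assumed log-SDs give apparent ratios from 0.87 to 1.15 and a false-significance rate from 5% (equal spread, no bias) to 75%. Either a false saving or a false excess is possible. Cost is more exposed than minutes under the referral mechanism examined.

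This rests on lognormal outcomes, assumed SDs and the planned facility-level design. It affects the secondary outcomes of cost and minutes. The primary outcome of counseling for drug-drug interactions and the stated sample size are unaffected. Confidence in the practical size is medium, because the documents give no SDs, wage rates or referral rates.

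**What to change.** State in section 4.6 that the reported effect for cost and minutes is the difference in arithmetic means, in dollars and minutes, whatever the skew. Estimate it in one of two ways:

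- the untransformed linear mixed model with the plan's two facility random effects, residual variance allowed to differ by group, and small-sample degrees of freedom or cluster-robust intervals; or
- a gamma mixed model with log link, followed by standardisation: predict each e-visit's cost under each group, average, and subtract.

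Keep any log-scale result as supportive and label it a ratio of geometric means.

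The cost is SAP wording and modest analysis work; the gamma option adds the standardisation step. Relative to the mean, intervals widen by √[((exp(s_A²) − 1) + (exp(s_P²) − 1))/(s_A² + s_P²)]. This is about 10% if both log-SDs are 0.6 and √(0.433 + 0.896)/√(0.36 + 0.64) = 1.15, or 15%, for 0.6 vs 0.8. With heavier skew the same formula gives 26% for 0.8 vs 1.0 and 31% if both are 1.0. With only 17 facilities, bootstrap intervals alone may be unstable, hence the small-sample correction.

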For the exploratory outcomes, patient care experience will be evaluated by surveying a sample of patients selected at random in the service areas in the Pharmacist Care and AFM Pool Care groups. We have designed a short survey that takes no more than 5 to 10 minutes to complete. The survey will be fielded by email, mail, and telephone. Due to the fact that we are asking about a specific care experience and patients' recall fades quickly after 2 weeks, we will field the survey using all 3 modes in a relatively efficient sequence. A letter containing a description of the study, language regarding informed consent and confidentiality, and the survey will be sent by mail on day 11 after the e-visit, and an email with a link to the online version will be sent on day 14. Telephone administration will be attempted (up to 4 attempts total) starting on day 17 for those who have not replied to the paper or online survey. A small gift to thank patients for considering participation will be included in the mailing. Responses will be treated as confidential and data will be aggregated, with no individual identifiers associated with data presented in reports.

Patient-reported outcomes will be reported on a 5-point scale and will include:

- a. Satisfaction with the overall quality of care
- b. Satisfaction with the timeliness of care
- c. Confidence in the care provided

Clinician satisfaction with the process of care will be evaluated by surveying all pharmacists on the regional team providing Pharmacist Care, plus the AFM site leads for Paxlovid e-visits in the service areas participating in the study. Because the AFMs in each service area cross-cover the Paxlovid e-visit requests from all facilities in that service area, it will not be possible to survey front-line AFMs in the two groups separately, and it would not be productive to ask the AFMs about their experience with Pharmacist Care because they would typically only have direct experience with Pharmacist Care if a problem arose that required their attention.

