Patient satisfaction and other care experience scores will be compared between the study groups using linear mixed effects regression with log transformation if needed for skewed data, with analyses paralleling that described for the other secondary outcomes.

For all aims, secondary analyses will assess variation in the estimates of treatment effect by age, race/ethnicity/language group, and comorbidity score group (high, medium, low) via stratification by level of the potential effect modifier. These stratified analyses will inform the fitting of regression models with appropriate cross-product terms between the potential effect modifier and study group indicator variable, allowing for a more formal assessment of heterogeneity in treatment effect.

A service area or facility may drop out before completion of the study if they were assigned to AFM Pool Care but add local pharmacist management, thus diverging from their assigned group. Paxlovid e-visits from such a service area or facility will be censored as of the dropout date (the date that local pharmacist management began).

Tests of significance will be two-tailed with an alpha of .05. No Bonferroni or other formal correction for multiple comparisons will be used, but results will be interpreted with the multiple testing issue in mind.

4.8. Sample size and power. To estimate the available sample, we extrapolated from April 2023. This was a month when COVID-19 incidence was low to medium; 4900 e-visits for Paxlovid were made across the 15 KPNC service areas. Based on this, an average of 1089 e-visits occur per week during low to medium COVID-19 incidence periods. However, e-visits that need to be answered on weekend days will not be eligible for pharmacist management; all of these will be excluded from the study. If 5 out of 7 e-visits occur on weekdays, an estimated 778 e-visits occur on weekdays during times of low to medium COVID-19 incidence.

This study will include 17 facilities that serve 872,200 adult members, or 25% of the 3.55 million adult members in the region. Each week, the estimated number of e-visits eligible for study is 25% of 778, or 195. Assuming an 8-week evaluation period, the estimated sample size is 1,560, or 92 patients in each of the 17 clusters.

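### The conditional log transformation does not suit the 5-point satisfaction items: if they are coded 5 = best and answers cluster at the top, it increases the skew it is meant to remove

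*Combined protocol and SAP*

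**What the plan says.** Section 4.5 (Data collection) lists three patient-reported items: overall quality, timeliness, and confidence in care. It states: "Patient-reported outcomes will be reported on a 5-point scale and will include" these three. No anchors, coding direction or expected distribution are given.

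Section 4.6 (Statistical analysis plan) compares them between groups "using linear mixed effects regression with log transformation if needed for skewed data". It does not say what would make the transformation necessary. No other method for skewed satisfaction scores is named: no ordinal model, no top-category analysis, no reflection of the score.

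Section 4.8 (Sample size and power) describes the same outcomes as "satisfaction scores, which are measured on a continuous scale". On sample size it says: "We aim to collect completed surveys from 200 patients in each of the two study groups". On the detectable difference: "We will be able to detect effect sizes of .31 relative to a standard deviation of 1". Section 4.6 adds: "Tests of significance will be two-tailed with an alpha of .05".

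Section 4.4.1 lists patient satisfaction as a secondary outcome. Section 1 (Aim 3) and section 4.5 treat it as exploratory.

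**The concern.** A log shortens a long right tail. It is a natural tool for positive, unbounded quantities such as minutes or cost. A 5-point rating is bounded and has five ordered values. If 5 is the best answer and most patients are satisfied, the long tail is on the left, and a log stretches it. The plan's only stated response to skew would then make the skew worse in the very situation that triggers it.

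The log also reweights the steps of the scale: a move from 1 to 2 counts about three times a move from 4 to 5. A few very dissatisfied patients would carry more of the comparison, and the difference between satisfied and very satisfied would carry less. Aim 3 hopes to find comparable satisfaction, so an avoidable loss of sensitivity would be unwelcome there.

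Because the coding direction and the criterion for transforming are both open, the scale of analysis would be settled only after the data are seen.

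**Working it through.** **1. The plan's own figure.** Inputs from the documents: 200 completed surveys per group, 17 facilities (section 4.1), ICC 0.01 (section 4.8), two-sided alpha 0.05. Section 4.8 states no power for the survey; I assume 80%, as it gives for Aims 1 and 2.

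- Surveys per facility: 400/17 = 23.5
- Design effect: 1 + (23.5 - 1) × 0.01 = 1.225
- Effective number per group: 200/1.225 = 163.2
- Detectable effect: (1.960 + 0.842) × sqrt(2/163.2) = 0.310 SD

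The stated 0.31 reproduces. Without clustering it would be 0.280.

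**2. Step sizes on the log scale.** ln(2/1) = 0.693, ln(3/2) = 0.405, ln(4/3) = 0.288, ln(5/4) = 0.223. The ratio of first to last is 0.693/0.223 = 3.11.

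**3. Skewness, 5 = best.** The distributions are assumptions. Skewness is Σp(s - m)³ / [Σp(s - m)²]^1.5, with s the score or its log and m its mean.

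| % in categories 1 to 5 | Raw | Logged |
|---|---|---|
| 5/5/10/30/50 | -1.40 | -2.29 |
| 3/5/12/35/45 | -1.27 | -2.36 |
| 3/4/8/25/60 | -1.72 | -2.75 |
| 3/3/6/18/70 | -2.15 | -3.14 |
| 2/2/4/12/80 | -2.85 | -3.97 |

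In 40,000 random distributions with percentages rising to the top category, the log made skewness more negative every time.

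**4. Power at the planned effect, 5 = best.** For each of the last four patterns, the comparison group is a proportional-odds shift, up or down, sized to 0.31 SD on the raw score. Power is Φ(d × sqrt(163.2/2) - 1.96), with d the standardised difference on the scale analysed.

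- Raw: 0.31 × 9.03 = 2.80; Φ(0.84) = 80%
- Logged, 3/4/8/25/60 shifted up: d = 0.270; 0.270 × 9.03 = 2.44; Φ(0.48) = 68%
- Logged, all four patterns, both directions: d = 0.269 to 0.277, power 68% to 71%

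**5. Other kinds of difference, base 3/4/8/25/60.**

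- 20 percentage points moved from 4 to 5: d = 0.200 raw and 0.132 logged; power 44% and 22%
- 3 percentage points moved from 1 to 4: d = 0.100 raw and 0.147 logged; power about 14% and 26%

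So the log costs power when the difference is at the top of the scale and gains it when the difference is at the bottom.

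**6. Coding 1 = best.** Reversing 5/5/10/30/50 gives skewness 1.40 raw and 0.64 logged. Reversing 3/4/8/25/60 gives 1.72 and 0.96, and power at 0.31 SD rises from 80% to 85-86%. Reversing the code of an untransformed score only changes the sign of the mean difference, whereas the logged result depends materially on the coding.

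**The case against.** The strongest reply is that the log is conditional. The default is an untransformed linear mixed model, and an analyst who saw the log worsen the skew could keep it. Linear models for 5-point items are common and give a readable mean difference. With 1 = best the log reduces the skew and raises power. All of this stands, and it is why the harm is stated conditionally. It does not remove the defect: the plan leaves the coding and the trigger open, so whether its rule helps or harms is not settled in advance.

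Four stronger readings are tempting, and the documents do not support them.

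- *The satisfaction comparison will lose power.* This needs top-heavy answers, 5 = best coding and a decision to transform, none of which is documented. Even then, step 5 shows a case where power rises.
- *The transformation can reverse the result.* This is arithmetically possible: 5/5/10/30/50 against 10/3/5/20/62 gives raw means 4.15 and 4.21 but geometric means 3.92 and 3.86. But these differences are +0.05 SD and -0.03 SD, which this survey could not distinguish from zero. Among random top-heavy pairs 4.5% reversed, none with a difference above about 0.14 SD, and no proportional-odds shift reversed.
- *The stated 0.31 SD no longer applies.* Section 4.8 gives a standardised effect and does not tie it to the raw score. The calculation holds for 0.31 SD on whichever scale is analysed. What changes is that a shift of 0.31 SD on the rating is a smaller standardised shift on its log.
- *A proportional-odds model must become the main analysis.* That is a reasonable preference, but the defect does not require it. The planned linear model without the log is adequate.

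**Conclusion.** The concern holds in conditional form. The only stated remedy for skew is ill-suited to a bounded 5-point item. If the items are coded 5 = best and answers are top-heavy, the log roughly adds one unit of negative skewness (0.9 to 1.1 in the patterns shown). For an even shift at the planned effect it costs about 9 to 12 points of power (80% to 68-71%). These sizes rest on assumed distributions, 80% planned power, ICC 0.01 and 17 clusters. With 1 = best, or with differences mainly in the lowest categories, the log gains power instead.

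Under either coding, a difference in mean log rating amounts to a ratio of geometric means of category labels, which is hard to use in an operational decision.

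Severity is minor. Satisfaction is secondary in one section and exploratory in others, and the primary, cost and time results are unaffected.

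**What to change.** In section 4.6, delete the log option for the 5-point items. State that they are analysed untransformed with the planned linear mixed model, reporting the mean difference with its interval, whatever the skew. In section 4.5, state the coding direction and the anchors. In section 4.8, describe the scores as 5-point ratings analysed as numeric scores, not as continuous measurements.

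Pre-specify one sensitivity analysis that respects the scale: either a mixed-effects ordinal logistic model or the percentage in the top category by group.

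The cost is a few sentences and a little more analysis, with no new data. If the ordinal model is chosen, its proportional-odds assumption has to be checked, and fitting it with two facility random effects on about 400 responses may be awkward; the top-category percentage is the simpler choice.
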